The preoperative and postoperative care for these patients is standardized. The surgical procedure is minimally invasive, performed through 3-4 small incisions, usually no larger than 3cm each. The hospital inpatient recovery is typically for 3-5 days, with regular scheduled postoperative visits at 2-3, 6-7 weeks, and 12-14 weeks from surgery. The timing of this first visit is specified so that a decision can be made as to whether the patient can proceed with additional treatment, such as radiation to the operated extremity, or chemotherapy. The key parts of this assessment include inspecting the surgical wounds for signs of infection and assessing the adequacy of soft tissue healing. In addition, the radiographic studies (x-rays) of the extremity are viewed by the physician. The time required for a surgeon to make this assessment for uncomplicated cases is typically short, averaging 5-7 minutes.

The post-operative follow-up visit utilizes standardized tools to establish patient-centered outcome data with a direct impact on the individual survivor as well as contributing to a dataset for predicting functional outcomes for all bone cancer survivors. However, only one-third of those seen are from local areas, and surveillance of persistent, late effects following surgery is suboptimal. Numerous obstacles limit both the patients' ability to attend face-to-face appointments (cost of travel, impaired mobility), and the providers' ability to collect patient-centered outcome data (clinic capacity). At our clinic, data show that approximately 30% of our patients miss an appointment in the post-operative period. A missed follow-up appointment prevents medical intervention needed to enhance survivorship and reduces data collection, which in turn, makes it difficult to accurately predict outcomes over time for future bone cancer survivors.

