Once the adaptation of the face-to-face follow-up to the mobile format has been verified, we will move to the limited efficacy testing (Objective 2/Specific Aim 3). A group of 40 patients that fit the inclusion criteria and have completed the informed consent process will be enrolled in the study. Participants will be enrolled in either a control group (n=20) or to the mobile surveillance group (n=20). The control group will have face-to-face follow up visits with no mobile surveillance at the appropriate time points. The mobile surveillance group (n=20) will have both face-to-face visits and additional data obtained using mobile devices. Patients in both groups will complete the same set of outcome measures. These measures will be administered at the following time points, 2, 6, 12, and 24 weeks.

Patients in the mobile surveillance group will complete an assessment using a mobile device at home during the week after their scheduled clinic visit at 2, 6, 12 and 24 weeks (see **Table 1** below). The mobile device data is in addition to data gathered at face-to-face clinical appointments, thereby adding outcome data and enhancing surveillance overall. Participants in the mobile surveillance group will take videos using the mobile devices and upload the data over the encrypted network using the My MD Anderson secure email transmission. Participants will be provided with a mobile device (or tablet) that is enabled with a mobile hot spot for data transmission. For recovery of function, video sequences will be acquired by patients performing prescribed tasks that will be used to quantify functional status according to the MSTS, ECOG, TUG, EVGS, FSST, NIH PROMIS GH Score. The participant's surgical wound will also be photographed using the mobile device. Quality of Life questionnaires and PROMIS SF v1 (Appendix G) surveys will be sent to the group for completion on their mobile device via REDCap Software or thru My MD Anderson email.

To ensure patient safety, participants in the mobile surveillance group will also engage in videoconferences at the prescribed timepoints using Vidyo or Zoom. All patient communication will be documented as follow-up notes in Clinic Station by the clinician.

Table 1. Study Design

Control Group n = 20	Mobile Surveillance Group Patients n = 20
Postoperative clinic visits	Postoperative clinic visits
2 weeks	2 weeks
6 weeks	6 weeks
12 weeks	12 weeks
24 weeks	24 weeks
Measures:	Measures:
Completion rates	Completion rates

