There are two measurements for limited efficacy testing, completion rate and patient satisfaction/acceptability. Among the set of questionnaires the patients need to complete, MSTS,

PI: [name], PhD

Protocol: 2015-0966

August 21, 2018

TUG, and PROMIS are considered the most important. A patient is considered having completed the follow-up assessment if the three outcomes are documented for the 2-, 6-, 12, and 24-week evaluations. We will then report the completion rates for each group for comparison.

We will report the patient satisfaction rate using patient satisfaction surveys for both the control and the study groups. When the sample size is 20, a two-sided 95% confidence interval (CI) for completion rate or satisfaction rate using the large sample normal approximation will extend at most 0.22 from the observed rate (nQuery Advisor 7.0). When the sample size in the group is 20, the 95% CI will extend 0.30 from the observed difference in rate assuming the rate is 0.50 for one group and 0.70 for the other group. The physician satisfaction rate for using mobile devices will be reported. We will also address the economic impact for using mobile devices. Repeated measures analysis may be utilized to evaluate change over time in the completion status or questionnaire scores for each method.

7.0 Data Management and Security:

All patient-reported and task performance outcomes and clinical data (including videos/photos) gathered under this protocol will be stored in a password-protected database. Data will not be transferred to laptop computers that are removed from the institution. Identifiers (name, medical record number) will be collected but will be replaced by study numbers in the analytic file. The key linking these numbers will be retained in a locked file by the investigator.

Data (including videos/photos) using mobile devices or tables will be encrypted by the IT department securely transferred using MY MD Anderson secure email to the research team.

Only MDACC personnel designated by the Principal investigator will have access to study records/data. These personnel will be fully trained to maintain the confidential nature of the patient health information. Paper records will be stored in locked files inside a locked office. External storage will be password protected.

Study data will not be shared with any individuals or entities that are not involved in the study. These data will be used only for research purposes and for this research study.

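### Optional, minor: use Wilson and Newcombe intervals rather than the normal approximation at 20 per group; the printed 0.22 and 0.30 still hold

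*Combined protocol and SAP*

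**What the plan says.** Section 6.0, Limited Efficacy Testing, has two measures: completion rate and patient satisfaction/acceptability. For a single rate in a group of 20, the two-sided 95% interval is given as "using the large sample normal approximation will extend at most 0.22 from the observed rate". For the comparison, with planning rates of 0.50 and 0.70, the plan says that "the 95% CI will extend 0.30 from the observed difference in rate". The normal approximation is the only interval method named anywhere in the protocol. No method is named for the difference.

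On reporting, the section says "We will then report the completion rates for each group for comparison", and it also promises satisfaction results by group. It does not say separately which interval the final report will use.

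The group sizes, 20 control and 20 mobile surveillance, are in Section 4.0, Specific Aim 3. The one background figure on likely rates is in Section 2.0: "approximately 30% of our patients miss an appointment in the post-operative period".

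**The concern.** Twenty is a small sample for the Wald interval. Its coverage rises and falls sharply as the true rate changes and is below the nominal level on average, even at moderate rates. At high observed rates it gives limits above 1, and at 20 of 20 it reports no uncertainty at all.

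Completion and satisfaction are the two limited-efficacy measures, and these intervals are how the plan expresses what 20 patients can show. If the report follows the one method named, intervals labelled 95% would cover about 92% on average at moderate rates, and less at high ones. Nothing in the plan turns on a confidence limit, so the stake is accurate reporting and not a decision.

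**Working it through.** **Inputs.** n = 20 per group (Section 4.0, Specific Aim 3); two-sided 95%, so z = 1.96; planning rates 0.50 and 0.70 (both Section 6.0).

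**1. The plan's own figures.**
- Single rate, worst case p = 0.50: 1.96 × √(0.25/20) = 0.219, which rounds to 0.22.
- Difference: 1.96 × √(0.25/20 + 0.21/20) = 0.297, which rounds to 0.30.
- A pooled variance gives 0.304, also 0.30. A continuity correction gives 0.244 and 0.347, which do not match.

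Both figures are therefore right for the uncorrected normal approximation. For the difference, that method is inferred from the match.

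**2. Single-rate coverage.** For each true rate, the binomial probabilities of the outcomes 0 to 20 whose interval contains that rate are summed, then averaged over an even grid of 3,001 true rates.

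| True rates | Wald mean | Wilson mean | Wald minimum | Wilson minimum |
|---|---|---|---|---|
| 0.50–0.70 | 0.924 | 0.951 | 0.884 | 0.929 |
| 0.50–0.80 | 0.922 | 0.952 | 0.849 | 0.929 |
| 0.80–0.95 | 0.852 | 0.958 | 0.639 | 0.916 |

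By symmetry the last row also applies to 0.05–0.20. Over 0.50–0.70, coverage is below 0.93 at 62% of true rates for Wald and 6% for Wilson.

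Selected points:

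| True rate | Wald | Wilson |
|---|---|---|
| 0.50 | 0.959 | 0.959 |
| 0.69 | 0.887 | 0.949 |
| 0.70 | 0.947 | 0.975 |
| 0.85 | 0.819 | 0.978 |
| 0.95 | 0.639 | 0.925 |

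**3. Boundary.** The Wald upper limit is 1.006 at 17/20, 1.031 at 18/20 and 1.046 at 19/20. At 20/20 Wald gives 1.00 to 1.00 and Wilson gives 0.84 to 1.00. The chance of 17 or more out of 20 is 0.11 at a true rate of 0.70 and 0.41 at 0.80. The chance of 20/20 is 0.001 at 0.70, 0.01 at 0.80 and 0.12 at 0.90.

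**4. Does 0.22 survive?** The Wilson limits are [p + z²/2n ± z√(p(1−p)/n + z²/4n²)] / (1 + z²/n). At 14/20 they are 0.481 and 0.855, so the longer reach is 0.700 − 0.481 = 0.219. That is the largest over all 21 possible outcomes. Wilson is also narrower at the planning rates: total width 0.401 against 0.438 at 10/20, and 0.373 against 0.402 at 14/20. The exact (Clopper-Pearson) interval would reach 0.243 and average 0.971 coverage over 0.50–0.70, so 0.22 would no longer hold.

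**5. Does 0.30 survive?** Newcombe's method combines the Wilson distances. At 14/20 they are 0.2190 below and 0.1545 above; at 10/20 they are 0.2007 each way.
- Lower limit: 0.20 − √(0.2190² + 0.2007²) = 0.20 − 0.297 = −0.097.
- Upper limit: 0.20 + √(0.1545² + 0.2007²) = 0.20 + 0.253 = 0.453.

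The longer reach is 0.297, so 0.30 holds on that side.

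**6. Coverage for the difference (Wald, Newcombe).**
- At 0.50 versus 0.70: 0.942, 0.945.
- Mean with both rates in 0.50–0.80 (31 × 31 grid): 0.935, 0.948.
- Mean with both rates in 0.80–0.95: 0.928, 0.970.

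**The case against.** The strongest reply is that the quoted sentence states planned precision and does not commit the analysis to a method. That is true: use of Wald in the final report is an inference, for single rates as well as for the difference. It is the only method named, and fixing the method in advance removes the doubt.

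Second, at the plan's two named rates taken singly, Wilson does not do better. Coverage is identical at 0.50, and at 0.70 Wald (0.947) is closer to 95% than Wilson (0.975). This stands, but it is fragile, because at 0.69 Wald falls to 0.887. Over the 0.50–0.70 grid Wilson is closer at 65% of true rates, tied at 25% and further away at 10%.

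Third, the case for Newcombe is weaker. At the planning rates the gain is negligible. With both rates in 0.80–0.95 it largely exchanges under-coverage for over-coverage: the mean absolute deviation from 95% is 2.2 points for Wald and 2.0 for Newcombe. At moderate rates (0.50–0.80) the advantage is clearer, 1.5 points against 0.3.

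Fourth, the largest gains occur at high rates, and the documents do not predict them. That also stands. Finally, Wilson does not guarantee 95% either: its coverage is 0.925 at a true rate of 0.95 and about 0.90 at 0.973.

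**Conclusion.** The point holds as a minor, optional improvement. The plan's arithmetic is correct and nothing in it needs rescuing.

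For single rates at n = 20, moving from Wald to Wilson raises mean coverage by 0.951 − 0.924 = 0.027 over the planning range, and by 0.958 − 0.852 = 0.106 over 0.80–0.95. It also removes impossible limits and zero-width intervals. For the difference the benefit is modest at moderate rates, negligible at 0.50 versus 0.70, and marginal when both rates are high.

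This rests on two assumptions: that the final report would use the one interval method the plan names, and that true rates within each range are weighted evenly. The first cannot be settled from the text. The second makes the claim one about average coverage, not coverage at every rate.

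**What to change.** Replace the two precision sentences in Section 6.0, Limited Efficacy Testing, with wording such as:

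> Two-sided 95% CIs for completion and satisfaction rates will be Wilson score intervals; with 20 patients, the longer arm of the interval is at most 0.22. The CI for the between-group difference will use Newcombe's hybrid score method; with 20 per group and observed rates of 0.50 and 0.70, its longer arm is 0.30.

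The mention of the longer arm is needed because score intervals are asymmetric: at those rates the two arms of the difference interval are 0.297 and 0.253. The 0.30 should stay tied to observed rates of 0.50 and 0.70, since over all outcomes the longest Newcombe arm is 0.310, as is the Wald maximum.

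The cost is a wording change in Section 6.0. Design, sample size, data collection and both printed figures are unchanged.

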8.0 Human Subjects Protection:

Collection of Identifiers: Identifiers (including name, medical record number and basic information, such as demographics, type of cancer and surgical procedure) will be collected by MDACC study personnel designated by the Principal Investigator, but will be replaced by study numbers in the analytic file. This information is already documented and available in the routine medical record. The key linking these numbers and all study data will be stored on password-protected computers. Study-related documents will be retained by designated study staff in locked files. Participant-identifying information will be kept confidential and will be available only to the PI and relevant study staff who have been trained to maintain patient health information.

Training of Personnel: Only MDACC personnel designated by the Principal Investigator will have access to study records. These personnel will be fully trained to maintain the confidential nature of the patient health information. All of the study personnel have completed the institution's research and human subjects training.

Data Sharing: Study data will not be shared with any individuals or entities that are not involved in the study.

9.0 Reporting of Adverse Events:

This PI initiated study is a low-risk study. The participants in both groups will continue to have regular follow-up appointments as scheduled.

The following adverse events will be tracked by the PI:

PI: [name], PhD

Protocol: 2015-0966

August 21, 2018

- Possible postoperative complications including wound infection, wound dehiscence, thromboembolism, and hardware failure/breakage. Adverse events and complications detected via mobile device will be addressed by instructing the patients to be seen in the emergency room or clinic. In case the participant does not submit a video or pictures at the appropriate timepoints, the study coordinator will contact the participant by phone and assess for the above adverse events.
- In the event that a patient may experience an adverse event during evaluation using a mobile device (i.e. falls while performing physical therapy assessments), he/she will be directed to call 911 or present to the local hospital for treatment. The treating surgeon will be notified.

9.0 References:

1. Hortobagyi, G. N. (2007). A shortage of oncologists? The American Society of Clinical Oncology workforce study. *Journal of Clinical Oncology*, 25(12), 1468-1469. doi: 10.1200/JCO.2007.10.9397

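### The adverse event call in Section 9.0 does not ask about falls during home testing and is not triggered by a missed safety videoconference, so a fall can go unrecorded

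*Combined protocol and SAP*

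**What the plan says.** Section 9.0 opens its list with "The following adverse events will be tracked by the PI" and gives two bullets.

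- **First bullet:** "Possible postoperative complications including wound infection, wound dehiscence, thromboembolism, and hardware failure/breakage". The same bullet then provides for missing remote data by having a coordinator make a call, who "will contact the participant by phone and assess for the above adverse events". The condition that sets off this call is worded as follows: "In case the participant does not submit a video or pictures at the appropriate timepoints".
- **Second bullet:** an adverse event during evaluation with a mobile device. The example given is "falls while performing physical therapy assessments". In that case "he/she will be directed to call 911 or present to the local hospital for treatment. The treating surgeon will be notified".

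Section 4.0, Specific Aim 3, adds a separate contact: "To ensure patient safety, participants in the mobile surveillance group will also engage in videoconferences at the prescribed timepoints using Vidyo or Zoom". Table 1 lists the videoconference with the physician, for the same purpose, among the mobile group's items at each timepoint.

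**The concern.** The call is the only place where the plan tells someone to make contact and ask about adverse events. Its scope stops at the first bullet, while the event tied to the home tasks is in the second. Its trigger is missing research material, while the contact described as protecting patients is the videoconference. A participant who falls while attempting a task and sends nothing would be asked about wound, clot and hardware problems. One who uploads but misses the videoconference would not be called.

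Two things are at stake. The first is patient safety: the PI can track only falls that reach the PI. The second is what the study can report. Specific Aim 4 includes the ability to detect wound complications and adverse postoperative events. If falls are not asked about in a uniform way, a report that none occurred would mean only that none was volunteered.

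**Working it through.** No arithmetic decides this point. The check is to set the provisions side by side.

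**1. Scope of the call.** The events above the call sentence are wound infection, wound dehiscence, thromboembolism and hardware failure. The word *including* leaves that list open, but only to other postoperative complications. Falls during mobile evaluation come below the sentence, in a bullet of their own. Read literally, the call does not reach them.

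**2. Trigger of the call.** The trigger is a missing video or pictures. A missed videoconference is not named in Section 9.0 or in Section 4.0.

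**3. Where home exposure arises.** In the feasibility step, patients use the device while still in clinic. Home testing belongs to the mobile surveillance group: 20 patients x 4 timepoints = at most 80 planned home sessions. This is a count of opportunities, not of falls.

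**4. Other contacts that might reveal a fall.**

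| Contact | Source | Required to ask about falls? | Limit |
|---|---|---|---|
| Physician videoconference | Section 4.0, Table 1 | No | Order relative to the home tasks in that week is not stated |
| Clinician notes of patient communication | Section 4.0, Specific Aim 3 | No | Record what is said, and prompt nothing |
| Helper at home | Section 3.0 | No | Required for help with collecting the physical therapy measures; no reporting duty stated |
| Next clinic visit | Section 4.0, Table 1 | No | See step 5 |

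**5. Timing of the clinic visit.** Home sessions fall in weeks 2-3, 6-7, 12-13 and 24-25, and clinic visits at weeks 2, 6, 12 and 24. The interval from a home session to the next scheduled visit is:

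- after the first session: 6 - 3 = 3 to 6 - 2 = 4 weeks;
- after the second: 12 - 7 = 5 to 12 - 6 = 6 weeks;
- after the third: 24 - 13 = 11 to 24 - 12 = 12 weeks;
- after the fourth: no later study visit is listed.

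A visit is therefore scheduled before each later home session, but none follows the last one (20 x 1 = 20 of the 80). Section 2.0 also reports that about 30% of the clinic's patients miss a postoperative appointment, and no rule makes a home session depend on attending the visit before it.

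**6. Relay of a fall.** The second bullet says "The treating surgeon will be notified". It does not say by whom, when or by what route, including when the patient was treated at a local hospital.

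The PI is thus to track an event that the one prescribed inquiry leaves out and that no named person is assigned to report.

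**The case against.** The strongest reply is that falls are not outside the adverse event plan. One lead-in governs both bullets, so the PI tracks falls, and the surgeon is to be told of them. The call is a back-up. The videoconference is due at every timepoint, nothing makes it conditional on an upload, and all patient communication is to be documented. Someone who uploads but misses the videoconference has still sent task videos and a wound photograph, and Section 9.0 has a response for complications detected that way. All of this stands, and it limits the point to what *can* be missed. It does not close the gap, because no one is told to ask.

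A reader might infer more than the documents support:

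- **That the next home test simply goes ahead after a fall.** A clinic visit is scheduled before each later home session, a helper at home is an eligibility condition, and the Four Square Step Test needs clearance by the physical therapist. These safeguards are incomplete (no such clearance is stated for the Timed Up and Go or the gait video), but they exist.
- **That falls are the one harm the study causes, or that people who fall tend not to upload.** The first goes beyond the text, which offers falls only as its example. The second is plausible, but nothing in the documents shows it.
- **That 30% of home sessions would be lost to follow-up.** The 30% is a share of patients missing a clinic appointment, not a share of sessions. If it meant 30% of patients missing at least one of three or four independent visits, the per-visit rate would be 1 - 0.7^(1/3) = 11.2% or 1 - 0.7^(1/4) = 8.5%. Even that describes clinic attendance, not uploads.
- **That the study must show home testing to be safe.** The stated feasibility aspects are adaptation, limited efficacy testing and acceptability, and no fall rate is to be estimated.

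**Conclusion.** The point holds as a gap in scope and trigger. As written, the plan's only prescribed adverse event inquiry omits falls during home assessment, a missed safety videoconference prompts no contact, and no one is named to relay a fall treated elsewhere. A fall can therefore go unrecorded despite being on the PI's list. No frequency, bound or bias is claimed, since the documents give neither a fall rate nor an upload rate.

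The conclusion rests on a literal reading of the call sentence and on no unpublished procedure already covering falls. If staff already ask about falls, the text should say so. Because the remedy is cheap and bears on patient safety, it should be made.

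**What to change.** In Section 9.0, reconcile the two bullets:

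1. Replace the call's reference to the events above with: *all adverse events listed in this section, including any fall or injury while performing or attempting a home assessment, and the reason for non-submission*.
2. Make a missed videoconference a trigger for the call as well.
3. Ask the same fall question at each videoconference and clinic visit, and record the answer, including when it is no.
4. Name the role that reports a fall to the PI and to the treating surgeon, including a fall treated at an outside hospital.

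Any clinical step after a fall is for the investigators to decide, and none is proposed here. The question concerns home assessments, so the answers describe the mobile group and do not provide a comparison with the control group.

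The cost is protocol wording, one question within contacts already planned, and a few extra calls. The recorded fall count may rise, which would reflect better ascertainment. Sample size and analysis are unchanged.
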